7. STUDY DESIGN

STREAMS is a randomised, double-blind crossover study comparing IV treatment with autologous MSCs vs. suspension media in MS patients with regards to the number of adverse events and new MRI activity (measured as GEL) at 24 weeks. A secondary analysis will compare the number of adverse events and GEL at weeks 0-23 and 24-48 within each treatment group (see Figure 1).

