7.1 STUDY OUTCOME MEASURES

Primary endpoints:

- number, timing and severity of adverse events in the MSC treatment group will be compared to the placebo group;
- total number of GEL counted over month 1, 3 and 6 will be compared between treatment groups.

[figure not shown]
Secondary endpoints:

- volume of GEL identified over months 1, 3 and 6 will be compared between treatment groups.
- number of GEL counted over months 7, 9 and 12 (crossover re-treatment) compared between treatment periods (placebo vs. active treatment) for each patient.
- combined unique MRI activity (number of new or enlarging T2, or enhancing or re-enhancing lesions).
- number of relapses in MSC treatment group vs. placebo group in the first 6 months and after crossover re-treatment in the two groups (see below for the definition of a relapse).
- time to sustained progression of disability (RRMS group) (see below for definition of sustained EDSS progression) and proportion of progression-free patients.

- proportion of disease-free patients (i.e. patients without relapses) and progression of MRI activity in the two groups.
- changes in the Multiple Sclerosis Functional Composite (MSFC) score in MSC treatment group compared to the placebo group.
- effect of MSCs on the peripheral immune responses (for patients in the first phase of recruitment).
- effect of MSCs on delayed type hypersensitivity (Type 1V hypersensitivity) reaction as measured by the Mantoux test.

Given the exploratory nature of MSC use, no specific quantitative assumptions have been made about the outcomes measures.

[figure not shown]
Figure 1: Patient flow and study outline

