11.3.1. Non-serious AR/AEs

All such toxicities, whether expected or not, should be recorded in the toxicity section of the relevant case report form and sent to the study coordination centre within one month of the relevant AR/AE.

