13. STATISTICS AND DATA ANALYSIS

13.1 RATIONALE

The main aim of each national trial participating in this international collaborative effort, including the present one, is to assess the feasibility, safety and the toxicity of MSC infusion, as administered within this specific treatment protocol, in active MS. To fulfill this aim, all randomised patients receiving at least one MSCs infusion (or infusion media) will be followed for at least two years after the last study drug administration. All adverse events will be recorded and compared in the two treatment groups. Comparative analyses of the incidence of new GEL at MRI acquired on conventional 1.5 T MRI scans over 24 weeks will be conducted as well, to provide preliminary data on the activity of the experimental treatment. However, the main analyses of safety, toxicity and activity will be those on the entire data set obtained by pooling the results of all national trials, for an expected total of 160 randomised patients.

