13.3 EVALUATION OF PRIMARY OUTCOME VARIABLES

- Primary outcome: To assess the safety of intravenous therapy with autologous MSCs in MS patients. The safety of MSCs infusion will be evaluated including frequency, timing and severity of any adverse events in both MSCs and placebo treatment groups. A statistical comparison of the number of adverse events between treatment groups will be carried out using a chi-square test.
- Co-Primary outcome: To assess the activity of autologous MSCs in MS patients. The total number of gadolinium-enhancing lesions (GEL) at MRI at week 4, 12 and 24 will be compared between treatment groups using a Negative Binomial (NB) regression analysis, adjusting for the number of GEL at baseline.

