13.6 DATA ANALYSIS

The number of GEL counted over 3 MRI scans will be considered a NB variable and analysed using a NB regression model. The model will be adjusted for the number of GEL on the baseline scan and will include treatment group as covariate. The number of relapses during the study period will be analysed with a NB regression model. Time to event variables will be studied with the Cox proportional-hazards model and visualised using the Kaplan-Meier survival curves. Proportion of events in the two treatment groups will be analysed by the chi-square test.

A paired-data analysis will be run to compare the number of GEL during the placebo and during the treatment arm in the group originally randomised to placebo, using both a parametric mixed model with NB errors and a non-parametric Wilcoxon test.

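### Infusion toxicity is observed after one MSC and one media infusion in each completer, but the only stated adverse event test is an unpaired chi-square that does not use this within-patient comparison

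*Combined protocol and SAP*

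**What the plan says.** Infusions are given at weeks 0 and 24 (10.4) and the treatments are reversed at the second (9.2). Section 10.5 monitors every patient for three hours after study treatment. Section 10.6 lists criteria, any one of which counts as infusion-related toxicity.

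These events do enter the adverse event record. Section 11.3.1 says of non-serious events: "All such toxicities, whether expected or not, should be recorded in the toxicity section of the relevant case report form".

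The analysis text is as follows.
- 13.3, the most direct statement: "A statistical comparison of the number of adverse events between treatment groups will be carried out using a chi-square test".
- 13.6, in general terms: "Proportion of events in the two treatment groups will be analysed by the chi-square test".
- 13.1: "All adverse events will be recorded and compared in the two treatment groups". It adds that "the main analyses of safety, toxicity and activity will be those on the entire data set" pooled from all national trials, with 160 patients expected.
- 7.1, primary endpoint: "number, timing and severity of adverse events in the MSC treatment group will be compared to the placebo group". No window is given.
- Section 7 describes the trial as comparing treatments on "number of adverse events and new MRI activity (measured as GEL) at 24 weeks", and then: "A secondary analysis will compare the number of adverse events and GEL at weeks 0-23 and 24-48 within each treatment group".

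The one paired analysis in 13.6 concerns GEL, in the placebo-first group only. Section 13 describes no analysis of 10.6 toxicity as an outcome in its own right.

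**The concern.** An acute reaction within three hours of an infusion is the kind of outcome a crossover handles well: it is short-lived, and both treatments are seen in the same patient 24 weeks apart. The stated test does not use that, whichever way its window is read.

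- **At 24 weeks.** This is the likelier reading, because section 7 gives the second period a separate comparison. Second infusions, half of the MSC and half of the media infusions in completers, then stay out of the MSC v media comparison.
- **Over both periods.** Sections 7.1, 13.1 and 13.3 set no window and allow this. Each completer then appears in both groups as if two different people. A patient's two responses may well be correlated: one 10.6 criterion is a heart rate below 60, which the same patient could meet after either infusion.

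The section 7 comparison of weeks 0-23 with 24-48 does not fill the gap. Within one sequence, treatment and period change together. No test is named, and the two sequences are never combined.

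Safety is a primary outcome, and infusion reactions are the only harm of the MSC product that the risk section lists (14.1.6). At stake is how precisely the excess risk from the cells, over media alone, is estimated.

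**Working it through.** **The plan's own figure.** The only sample size is for GEL (13.2: mean 7.4, SD 11.4, 50% decrease, 80% power, 5%). With a negative binomial model, dispersion = (11.4² − 7.4)/7.4² = 2.238. Then n per arm = (1.960 + 0.842)² × (1/7.4 + 1/3.7 + 2 × 2.238)/(ln 0.5)² = 79.7, so 80 per arm and 160 in all. The 160 reproduces and is not in dispute. It supplies the 80 v 80 split used below (1:1 allocation assumed).

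**Inputs not in the documents.** No toxicity rate or within-patient correlation r is given. The rates and r below are assumptions. Tests are two-sided at 5%, and powers come from exact enumeration.

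**Reading 1: first infusions only, against both infusions (pooled 160, r = 0).** The columns are an uncorrected chi-square on 80 v 80; exact McNemar on 160 pairs; Mainland-Gart, which allows for period (Fisher's exact test on discordant pairs by sequence, 80 + 80); and Mainland-Gart when 10% miss the second infusion (72 + 72).

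| MSC v media | Chi-square 80 v 80 | McNemar 160 | Mainland-Gart 80 + 80 | Mainland-Gart 72 + 72 |
|---|---|---|---|---|
| 15% v 5% | 57% | 81% | 80% | 75% |
| 12% v 4% | 46% | 70% | 67% | 62% |
| 20% v 10% | 42% | 66% | 64% | 59% |

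Half-width of the 95% interval for the risk difference at 15% v 5%:
- First infusions: 1.96 × √[(0.15 × 0.85 + 0.05 × 0.95)/80] = 1.96 × √(0.175/80) = 9.2 points.
- Both infusions, r = 0: 1.96 × √(0.175/160) = 6.5 points.

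At r = 0 the gain comes from using twice as many infusions, not from the pairing itself.

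**Reading 2: all infusions, pairing ignored (160 v 160).** The joint probability of toxicity after both infusions is p₁p₀ + r√[p₁(1 − p₁)p₀(1 − p₀)].

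| | r = 0 | r = 0.2 | r = 0.4 |
|---|---|---|---|
| True size at 10% v 10% (nominal 5%) | 5.1% | 2.9% | 1.2% |
| Reported half-width, 15% v 5% | 6.5 | 6.5 | 6.5 |
| Correct paired half-width | 6.5 | 5.9 | 5.2 |
| Power, unpaired chi-square, 15% v 5% | 87% | 89% | 93% |
| Power, exact McNemar, 15% v 5% | 81% | 90% | 97% |

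For example, at r = 0.2 the discordant probabilities are 0.127 and 0.027, and 1.96 × √[(0.127 + 0.027 − 0.10²)/160] = 5.9 points.

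**UK trial (23; 12 v 11 in the first period assumed).** Exact 95% intervals for an MSC rate near 15%: 2/12 gives 2.1-48.4%; 4/23 gives 5.0-38.8%. The half-width for 15% v 5% is 1.96 × √(0.1275/12 + 0.0475/11) = 24 points on first infusions and 1.96 × √(0.175/23) = 17 points on both. Neither supports a useful test.

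**The case against.** Infusion toxicity is not a listed endpoint in 7.1. The events are recorded, and 13.3 promises frequency, timing and severity of adverse events by treatment, which is where a three-hour reaction would show. That is fair, and it rules out the stronger reading that toxicity goes uncollected or unreported. What remains is that 13.1 names toxicity as a main analysis and no method suited to two results per patient is given.

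A reader might also infer that second-period adverse events are discarded altogether. Section 7 plans a within-group comparison that uses them. They are absent only from the stated between-treatment test, and only on the 24-week reading.

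A reader might infer that ignoring the pairing creates false positives or always loses power. It does neither. With positive correlation the test is conservative, and at r = 0 the unpaired chi-square on all infusions has more power than exact McNemar (87% v 81%).

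It is tempting to add that reactions are swamped by 24 weeks of other events, including lumbar puncture effects. The documents do not support a figure for that: it would assume a test on patients with any event, whereas 13.3 compares the number of events.

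The power case depends on pooling, and the documents conflict. Section 13.2 assigns safety to up to 23 UK patients and pools for efficacy; 13.1 pools safety and toxicity too, and section 18 pools the primary outcomes. Any separate pooled plan is not among the documents. Finally, the rates are unsourced. If the background rate is higher, as a heart-rate criterion might make it, both methods do worse: at 30% v 20%, 32% for the 80 v 80 chi-square and 48% for Mainland-Gart on 160 pairs. The gain persists, but neither method is then well powered.

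**Conclusion.** The point holds, as an inefficient or mis-specified comparison of an outcome the trial already collects on both treatments in each completer. On the likelier 24-week reading, the cost in pooled data at an assumed 15% v 5% with no correlation is about 23 percentage points of power (57% v 80%), or about 18 with 10% missing the second infusion, and an interval about 40% wider (9.2/6.5 = 1.4). On the both-period reading, the cost is a misstated error: a nominal 5% test that runs at about 1% to 3% for correlations of 0.4 to 0.2, and an interval wider than it should be. For a harm outcome, both work against seeing a real excess clearly.

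The sizes rest on assumed rates and correlations, 1:1 allocation, and safety being pooled as 13.1 says. If 13.2 governs instead, the point reduces to precision of estimation in at most 23 patients. The within-patient comparison also assumes that a first infusion does not alter a three-hour reaction 24 weeks later.

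**What to change.** In 13.3, with a matching line in 13.6:
1. State the time window for the adverse event comparison.
2. Report 10.6 toxicity as yes/no per infusion, by treatment received and by period, with exact 95% intervals over all MSC and all media infusions.
3. In the pooled data, estimate the MSC v media difference within patient across both sequences, allowing for period, by Mainland-Gart or conditional logistic regression with a period term. Patients with one infusion count in the proportions but not in the pairs.
4. In the UK trial, make the proportions and intervals the result and claim no useful power for a test.
5. Reconcile 13.1 and 13.2 on whether safety is pooled.

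Keep the between-group comparison for other adverse events.

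The cost is a short paragraph; no new data or visits are needed. Allowing for period costs about 1 to 3 points of power against McNemar. The real price is the no-carry-over assumption. The breakdown by period can check it only weakly: it is imprecise and cannot separate carry-over from a treatment-by-period interaction.

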8.2 INCLUSION CRITERIA

Patients with clinically and radiologically active multiple sclerosis as defined by:

1. Diagnosis of MS:
 - a. Relapsing remitting MS (RRMS): ≥ 1 moderate-severe relapse **and** ≥ 1 GEL in past 18 months **or** ≥ 1 moderate-severe relapse and ≥ 1 new T2 lesion in past 18 months.
 - b. Secondary progressive MS (SPMS) with an increase of ≥ 1 EDSS point (if baseline EDSS ≤ 5.0) or 0.5 EDSS point (if baseline EDSS ≥ 5.5), in the previous 18 months **and** ≥ 1 GEL in past 18 months **or** ≥ 1 moderate-severe relapse and ≥ 1 new T2 lesion in past 18 months.
 - c. Primary progressive MS (PPMS) patients with positive oligoclonal bands (OCBs) in the cerebrospinal fluid (CSF) and an increase of ≥ 1 EDSS point (if base-line EDSS ≤ 5.0) or 0.5 EDSS point (if baseline EDSS ≥ 5.5), or quantifiable, objective evidence of equivalent progression in the previous 18 months **and** ≥ 1 GEL in past 18 months or ≥ 1 new T2 lesion in past 18 months.
2. Age 18 to 50 years.
3. Disease duration 0 to 10 years from diagnosis (inclusive).
4. EDSS 2.0 to 6.5 at screening evaluation.
5. ≥ 1 GEL on MRI within 6 months prior to harvesting.
6. Adequate culture of a subject's MSCs and their release for clinical use.

Justification for the inclusion criteria

Working definitions for active MS emphasise accumulation of disability, occurrence of relapses or a combination of both. Our aim is to identify a patient population who is at increased risk of continued progression and loss of function but has not accumulated advanced levels of neuronal injury or degeneration which could fail to show a treatment effect even if it exists. We have therefore formulated criteria to recruit patients with mild to moderate disability and evidence of ongoing inflammation (gadolinium-enhancing lesions) relatively early in the disease.

Each subject must generate MSCs suitable for clinical use otherwise the procedure will have no chance of benefit (section 10.3).

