9.2 RANDOMISATION PRACTICALITIES

All subjects will be randomised after the investigator has verified that they are eligible by the criteria (section 8). Randomisation will be carried out within a web-based system, made available to authorised researchers, by the Clinical Research Organisation (CRO) in charge: *Centro Clinical Trials, [contact] Email: [contact]*

Eligible patients will be randomised to receive immediate vs. delayed treatment with either autologous MSCs or equivalent volume of suspension media at baseline. At 6 months, patients and investigators will continue to be blinded to therapy, but treatments will be reversed (i.e. those who received initial MSCs will receive suspension media and vice versa).

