12.8 MRI PROCEDURES

12.8.1. Outline

All patients will be scanned at one site: the MS Society-funded 3T MRI scanner at the UCL Institute of Neurology. Scans will be acquired at weeks 0, 4, 12, 24, 28, 36 and 48. If drop-out occurs before the study ends, all remaining MRI scans will be obtained, if possible, at the scheduled time-points or if this will not be possible, at an unscheduled visit (exit visit). The MRIs will be analysed by [name] group at the Institute of Neurology but as the data will also contribute to the international collaborative effort, these MRIs will be anonymised and sent to the Medical Image Analysis Centre (MIAC), located in Basel, Switzerland which is being used for analysis of the primary outcomes.

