13.4 EVALUATION OF SECONDARY OUTCOME VARIABLES

Secondary outcomes: To gather preliminary information about the efficacy of the experimental treatment in terms of combined MRI activity, incidence of relapses and disability progression.

- The total number of GEL lesions at MRI at weeks 4, 12 and 24 in the group originally randomised to placebo will be compared with the number of GEL lesions at MRI at weeks 28, 36 and 48 following the infusion using a mixed effect generalised model with NB errors.
- The dependence on time of the total number of GEL at MRI will be analysed in the group originally randomised to active treatment using a mixed effect generalised model with NB errors.
- Combined unique MRI activity (new or enlarging T2, or enhancing or re-enhancing lesions). The total number of new or enlarging T2, or enhancing or re-enhancing lesions at MRI at week 4, 12 and 24 post-treatment will be recorded in the two groups using a Negative Binomial (NB) regression analysis with the treatment group as covariate.
- Number of relapses in MSCs treatment group vs. placebo group will be acquired and using a Negative Binomial (NB) regression analysis with treatment group as covariate
- Time to sustained progression of disability (RRMS group) will be analyzed with a Cox proportional-hazards model
- Proportion of progression-free patients in two groups will be compared with the use of a chi-square test (RRMS patients).
- Mean changes in Multiple Sclerosis Functional Composite (MSFC) score in MSC treatment group vs. placebo group compared to baseline will be analysed with a one-way ANOVA test.

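### The placebo-v-MSC comparison of GEL across periods is confined to the placebo-first group, where treatment and period cannot be separated; no contrast uses both randomised sequences

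*Combined protocol and SAP*

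**What the plan says.** Patients are randomised to one of two sequences, and at six months the treatments switch: "those who received initial MSCs will receive suspension media and vice versa" (section 9.2). "Scans will be acquired at weeks 0, 4, 12, 24, 28, 36 and 48" (section 12.8.1). The week-24 scan precedes the second infusion (section 12.2.1), so every patient has three scans per period, nominally 4, 12 and 24 weeks after each infusion.

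Two places announce period comparisons for both sequences. Section 7: "A secondary analysis will compare the number of adverse events and GEL at weeks 0-23 and 24-48 within each treatment group". Section 7.1 lists as a secondary endpoint the GEL count over months 7, 9 and 12, "compared between treatment periods (placebo vs. active treatment) for each patient".

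The methods treat the sequences differently:

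- Placebo-first. Under section 13.4 the total at weeks 4, 12 and 24 "will be compared with the number of GEL lesions at MRI at weeks 28, 36 and 48 following the infusion", using a mixed NB model. Section 13.6 adds a paired analysis to "compare the number of GEL during the placebo and during the treatment arm in the group originally randomised to placebo", by a mixed NB model and a Wilcoxon test.
- MSC-first. Section 13.4: "The dependence on time of the total number of GEL at MRI will be analysed in the group originally randomised to active treatment". This is also a mixed NB model, but no placebo-v-MSC contrast is named.

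No section combines the two sequences, names a period term or takes a position on carry-over. The co-primary GEL analysis (sections 13.3 and 13.6) is separate: it compares the randomised groups over weeks 4, 12 and 24, adjusted for baseline GEL.

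**The concern.** In the placebo-first group every placebo count comes from the first period and every MSC count from the second. Any change in lesion activity over the year is therefore absorbed into the apparent treatment effect, and no model fitted to that group alone can remove it. A natural fall would look like benefit; a natural rise would hide benefit.

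Either direction is possible. Patients must have at least one "GEL on MRI within 6 months prior to harvesting" (section 8.2), which favours a later fall. Disease-modifying therapy is barred throughout (section 8.4), which leaves room for a rise.

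A crossover has a remedy built in. The reverse sequence is randomised and scanned at the same weeks, so it measures the same drift with the treatments in the opposite order. The plan collects those data but does not use them in this contrast. What is at stake is how a before-after result is read: as support, or lack of support, for MSC when activity may only have drifted.

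**Working it through.** **1. Inputs and the plan's own figure.** Section 13.2 gives a mean of 7.4 GEL over three scans (SD 11.4), a 50% decrease, 80% power and a 5% level. The NB dispersion is k = (11.4² − 7.4)/7.4² = 122.56/54.76 = 2.238. With a two-sided test and 1:1 allocation (neither is stated), n per arm = (1.960 + 0.842)² × (1/7.4 + 1/3.7 + 2 × 2.238)/(ln 0.5)² = 7.849 × 4.882/0.4805 = 79.7. That rounds to 80 per arm, or 160 in total, which matches the plan. This figure rests on the first-period comparison, so nothing below changes it.

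**2. What each group estimates.** Let θ be the MSC/placebo ratio and π the second/first-period ratio without treatment. With no carry-over:

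- placebo-first, period 2 / period 1 = θπ
- MSC-first, period 2 / period 1 = π/θ

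The first ratio alone cannot separate θ from π. Dividing it by the second gives θ², and π cancels. If θ = 1 and π = 0.70, the placebo-first analysis shows a ratio of about 0.70 with no MSC effect.

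**3. Is drift likely?** Harvest is at week −8 (section 10.1), 12 weeks before the week-4 scan. The qualifying scan may be up to 26 weeks earlier still, so it lies nominally 12 to 38 weeks before week 4. Much of any selection-related fall may precede both windows. The documents give no figure, so drift is treated as an assumed range.

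**4. Planned Wilcoxon test, no MSC effect, natural fall.** Counts were simulated as Poisson with gamma variation between patients and between periods. The mean was 7.4 and total dispersion 2.238. The assumed within-patient correlation was 0.49-0.67. Allocation was assumed to be 12/11 here and 80/80 pooled. There were 10,000 simulated trials per setting (12/11) or 4,000 (80/80).

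| Assumed fall | Rejects, 12 patients | Rejects, 80 patients |
|---|---|---|
| none | 5% | 5% |
| 10% | 5-6% | 9-14% |
| 20% | 7-9% | 29-41% |
| 30% | 12-15% | 59-77% |

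Widening the correlation to 0.26-0.82 gives 9-22% and 43-93% at a 30% fall. A separate simulation with 11 placebo-first patients and a different split of the dispersion gave 8-9% at a 20% fall and 11-17% at 30%. With 80 patients it gave 27-50% and 56-87%. Only the Wilcoxon test was simulated. The planned mixed NB model in the same group is confounded by step 2, but its rejection rate was not computed.

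**5. True halving, natural rise of 10/20/30%.** Power of the planned Wilcoxon test falls from 31-42% without drift to 23-33%, 19-26% and 15-21% with 12 patients. With 80 it falls from 99-100% to 95-99%, 88-96% and 74-90%.

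**6. Two-sequence contrasts, no carry-over.** A rank test comparing within-patient period differences between the sequences rejects falsely in 4-5% (12/11) and 4-6% (80/80) for drifts from −30% to +30%. With 12/11 it has 50-71% power for a halving over that range. An NB mixed model on period totals, tested at drifts of −30% and +30%, rejects falsely in 6-9% (12/11) and 4-7% (80/80), with Monte Carlo error of about 1-2 points. The rank test is therefore the safer main version at this size.

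**7. Carry-over.** Suppose a true ratio of 0.50. If half the reduction persists, the MSC-first second period runs at 0.75 of its untreated level, and the contrast reads √(0.5 × 0.5/0.75) = 0.58. If all of it persists, it reads √(0.5 × 0.5/0.5) = 0.71. Rank-test power with 12/11 and no drift falls from 54-71% to 37-51% and 19-24%.

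**The case against.** The strongest defence is that the placebo-first restriction is a sensible way to avoid carry-over. Section 9.2 frames the randomisation as immediate against delayed treatment, and no washout separates the infusions. Sections 5.2.1 and 5.2.2 describe long cell survival after transplantation in sheep, and repair mechanisms. The second period of the MSC-first group may therefore not be a clean placebo period. If the effect persists in full, the two-sequence rank test has 19-24% power against 31-42% for the planned Wilcoxon test without drift. This stands as a reason to add the new contrast and not to substitute it. The documents do not give it as their reason, however, and it does nothing about period confounding.

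Second, randomisation already answers the efficacy question in the first period, and section 13.4 calls the secondary information preliminary. That stands, and it limits the weight of the point.

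Third, the MSC-first group is not ignored. A reader might infer that it goes unanalysed, but the section 13.4 time model can reasonably be taken as the within-group comparison of section 7, and a shared drift might be visible there. It would be mixed with any waning or persisting MSC effect, and the plan never sets it against the placebo-first result. The gap is the missing combined contrast.

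Fourth, the drift is assumed and the effect at about 12 patients is modest. Both are correct.

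**Conclusion.** The point holds as a cheap improvement to a secondary analysis. The placebo-first before-after ratio is treatment multiplied by period, and the plan leaves out the randomised comparison that would separate them. For an assumed natural fall of 20-30% and no MSC effect, the Wilcoxon test rejects in about 7-15% of trials with 12 placebo-first patients. With 80 it rejects in about 29-77%. The larger figures apply only if this outcome is pooled, which section 5.2.4 says and section 18 leaves open. All these figures depend on the assumed drift, the assumed correlation and the plan's mean and SD.

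Two stronger readings are tempting. One is that the trial's efficacy conclusion is compromised. The documents do not support this, because the co-primary comparison is between randomised groups within the first period. The other is that selection on a recent lesion will produce a false positive. The documents give neither size nor direction of drift, the timing in step 3 places much of any such fall before both windows, and a rise is also possible.

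**What to change.** 1. In sections 13.4 and 13.6, label the placebo-first before-after analyses descriptive.
2. Add a two-sequence contrast on period totals (weeks 4 + 12 + 24 against weeks 28 + 36 + 48). At this trial's size, make the main version a rank test of within-patient period differences between the randomised sequences. As a supporting analysis, or for pooled data, fit an NB mixed model on the period totals with treatment, period and baseline GEL as fixed effects and patient as a random effect. This would also supply the comparison promised in section 7.1.
3. State that the contrast assumes no carry-over, is biased towards no effect if MSC effects persist past week 24 (a true 0.50 reads as about 0.58 with half persistence and 0.71 with full persistence), and does not replace the first-period comparison.

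The cost is a few lines of text, one model of a type already planned and one rank test. No extra scans or patients are needed. The downside is the carry-over bias in item 3.
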